10.4 Performance Status

Patients will be graded according to the Zubrod Performance Status Scale.

POINT	DESCRIPTION
0	Fully active, able to carry on all pre-disease performance without restriction.
1	Restricted in physically strenuous activity but ambulatory and able to carry out work of a light or sedentary nature, e.g., light housework, office work.
2	Ambulatory and capable of self-care but unable to carry out any work activities; up and about more than 50% of waking hours.
3	Capable of limited self-care, confined to bed or chair more than 50% of waking hours.
4	Completely disabled; cannot carry on any self-care; totally confined to bed or chair.

10.5 Progression-Free Survival

From date of registration to date of first documentation of progression or symptomatic deterioration (see Section 10.2e), or death due to any cause. Patients last known to be alive without report of progression are censored at date of last contact.

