1.3 Secondary Objectives

- a. To estimate overall survival and progression-free survival.
- b. To assess the toxicity profile of the recommended Phase II dose.
- To assess response (complete and partial, confirmed and unconfirmed) of patients enrolled on each Phase I portion.

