7.11 Follow-Up Period

All patients will be followed until death or 3 years after registration, whichever occurs first.

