9.3 Study Calendar – Phase II D+T+G (contd.)

			Сус	le 1			Cyc	cle 2			Cyclo	e 3 + β		Follow-Up Prior to Progression	At Time of Progression	Post- Progression Follow Up Ψ
REQUIRED STUDIES	PRE-	Wk	Wk	Wk	Wk	Wk	Wk	Wk	Wk	Wk	Wk	Wk	Wk			
OTOBIES	STUDY	1	2	3	4	5	6	7	8	9	10	11	12			
X-RAYS & SCANS																
CT or MRI Scan of the brain	Х															
CT or MRI ¥	X									Х				X£	Х	
ECHO or MUGA	Х									Χπ						
ECG	Х															
SPECIMEN SUBMISSION																
Paraffin-Embedded Tissue/Slides (Fresh Frozen Tissue																
If Available)	Х			ΧФ											X	
Plasma and Buffy Coat ®	Х									Х					X	
TREATMENT																
Dabrafenib ∑		Х	Х	Х	Х	Х	Х	Х	Х	Х	Х	Х	Х			
Trametinib -		X	X	Х	X	Х	X	X	X	Х	Х	X	X			
GSK2141795 r		Х	Х	Х	Х	Х	Х	Х	Х	Х	Х	Х	Х			

Click here for footnotes.

NOTE: Forms are found on the protocol abstract page of the SWOG website (www.swog.org). Forms submission guidelines are found in Section 14.0.

Footnotes:

- ¥ Disease assessments must be performed after every two cycles of treatment using the same method as baseline and must be documented on the Follow-Up Tumor Assessment Form (RECIST 1.1). A response must be confirmed by a second determination at least 4 weeks after a complete or partial response has been noted.
- \sqrt{V} Ophthalmic exam must be performed at baseline. Follow-up exams are to be performed as clinically indicated.
- ** Dermatology exams are required every 2 months throughout treatment, and every 2 months through 6 months after discontinuation of dabrafenib or until the start of another anti-neoplastic therapy.
- π On treatment echocardiogram should be obtained every 2 months for all patients.
- ☐ Patients known to be HIV + must not be on antiviral agents and must have CD34 counts ≥ 500 mm³ (see Section 5.1t).
- Δ See Sections 5.1u and 7.2b.
- B Protocol treatment assessments will continue on this schedule until any one of the criteria in Section 7.8 is met.
- £ Once off protocol treatment, disease assessments must be performed every 8 weeks until disease progression.
- Ψ After disease progression (see Section 10.2), follow-up for survival status must be performed every 3 months for the first year, then every 6 months for a total of 3 years from the date of registration or death, whichever is first.

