11.4 Analysis of Secondary Endpoints

The Phase II Portion will include estimating overall survival, progression-free survival, and toxicity rates. Assuming 33 eligible patients are enrolled, this will be sufficient to estimate overall survival, progression-free survival, and toxicity rates to within \pm 17% (95% confidence interval). Assuming 33 eligible patients overall, any toxicity with at least a 5% chance of occurring has a 82% chance of being observed at least once. In addition, to assess safety and feasibility in both the Phase I and Phase II Portions of the trial, descriptive statistics will be presented for the number of patients requiring dose reduction, interruption or discontinuation and the percentage of dose delivery.

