Follow-Up Form (if patient was off treatment) documenting date, site and method for determining progression.

f. WITHIN 14 DAYS OF DISCONTINUATION OF TREATMENT SUBMIT:

Off Treatment Notice

S1221 Treatment Form

\$1221 Adverse Event Form.

g. AFTER OFF TREATMENT, SUBMIT EVERY 3 MONTHS FOR 1 YEAR AND 6 MONTHS UP TO 3 YEARS FROM DATE OF REGISTRATION:

Follow-Up Form

Late Effects Form (if prior to treatment for progression or relapse or a second primary, and prior to non-protocol treatment, the patient experiences any severe [Grade \geq 3] long term toxicity that has not been previously reported).

h. WITHIN 4 WEEKS OF KNOWLEDGE OF DEATH SUBMIT:

Notice of Death **and all of the items listed in Section 14.4f** (if the patient was still on protocol treatment) or Follow-Up Form (if the patient was off protocol treatment) documenting death information.

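### PFS is censored at last contact, not last disease assessment, so it can be biased upward if patients stop scans but stay in follow-up

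*Combined protocol and SAP*

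**What the plan says.** PFS is a secondary objective (Section 1.3: "To estimate overall survival and progression-free survival"). Section 11.4 plans to estimate it in Phase II, and Section 11.5 uses it in exploratory marker analyses.

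Section 10.5 runs PFS "From date of registration to date of first documentation of progression or symptomatic deterioration", or to death from any cause. For everyone else: "Patients last known to be alive without report of progression are censored at date of last contact". Section 10.6 applies the same last-contact rule to time to death.

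The Phase II calendar (Section 9.3) sets the scans. On treatment: "Disease assessments must be performed after every two cycles of treatment using the same method as baseline", which is 2 × 28 days = 8 weeks. Off treatment: "Once off protocol treatment, disease assessments must be performed every 8 weeks until disease progression".

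Follow-Up Forms have a different calendar. Section 14.4, item g, asks for them after treatment ends every 3 months for a year, then every 6 months, up to 3 years from registration. Section 7.11 adds: "All patients will be followed until death or 3 years after registration, whichever occurs first".

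No section says how PFS handles missed assessments, or a death or progression that follows them.

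**The concern.** A contact shows whether a patient is alive, so last contact is a sound censoring date for survival. It does not show whether the disease has progressed. Section 10.2 defines progression by lesion measurements, unequivocal worsening of non-measurable disease, new lesions, or death due to disease. A patient who has stopped scans but still appears on Follow-Up Forms may have progressed without anyone knowing, yet stays at risk and event-free in the Kaplan-Meier estimate until last contact or death.

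The error runs in one direction, there is no control arm to share it, and the confidence interval does not show it. At stake is the accuracy of a secondary estimate and of the marker analyses that reuse it.

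**Working it through.** **The plan's own figure.** Half-width of a 95% interval for a rate with 33 patients: 1.96 × √(0.5 × 0.5 / 33) = 0.1706, which reproduces the ±17% in Section 11.4.

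**Inputs.** From the documents: scan interval W = 56 days = 1.84 months (Section 9.3); follow-up to 36 months (Section 7.11); accrual of 2–3 per month, so 33 / 2.5 ≈ 13 months (Section 11.1); median PFS of 3.6 months, used only as a plausible scale (Section 2.0). Assumed, because the documents are silent: exponential times; median survival after progression of 4 or 8 months; a share f of 5–30% who stop scans but stay in contact.

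**Step 1: everyone scanned.** The progression rate is a = ln 2 / 3.6 = 0.1925 per month. The last scan before 6 months is at 3W = 5.52 months, and exp(−0.1925 × 5.52) = 0.345. Allowing for deaths between that scan and 6 months gives 34.4–34.5%. For 12 months the last scan is at 6W = 11.04, and the result is about 12%.

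**Step 2: a patient who stops after scan k.** Under the last-contact rule this patient counts as progression-free at time t if there was no progression by scan k and the patient is alive at t:

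exp(−a·kW) × G(t − kW), with G(x) = (a·e^(−bx) − b·e^(−ax)) / (a − b) and b = ln 2 / (median survival after progression).

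At t = 6 months, for k = 0, 1, 2, 3:
- median 4 months: 0.701, 0.578, 0.459, 0.344; mean 0.520
- median 8 months: 0.823, 0.632, 0.474, 0.345; mean 0.569

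**Step 3: bias at 6 months** = f × (mean − value with everyone scanned). With k = 0–3 equally likely, the difference is 0.520 − 0.344 = 0.176 or 0.569 − 0.345 = 0.224. If stopping is instead uniform over the first 6 months, k = 0, 1, 2 each have weight 1.84/6 = 0.307 and k = 3 has 0.08. The means become 0.560 and 0.620, and the differences 0.216 and 0.275.

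| Share stopping scans | k = 0–3 equally likely | Uniform over 6 months |
|---|---|---|
| 0% | 0 | 0 |
| 5% | +0.9 to +1.1 | +1.1 to +1.4 |
| 10% | +1.8 to +2.2 | +2.2 to +2.7 |
| 20% | +3.5 to +4.5 | +4.3 to +5.5 |
| 30% | +5.3 to +6.7 | +6.5 to +8.2 |

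So 6-month PFS rises from about 34% to about 37%, 39–40% and 41–43% for 10%, 20% and 30% stopping under the uniform pattern. A simulation of 150,000 patients per scenario (k = 0–3 equally likely) agrees to within rounding and sampling error at full follow-up. In it the observed median moves from 3.7 to at most 5.5 months, one scan interval.

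**Step 4: what each rule removes.** Bias in points from the same simulation, at 30% stopping. Ranges cover the two post-progression medians.

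| Minimum follow-up | Time | Last contact (plan) | Last assessment, living patients only | Also deaths after two or more missed scans |
|---|---|---|---|---|
| 3 months | 6 mo | +4.7 to +6.1 | +0.6 to +0.8 | −1.0 to −0.6 |
| 3 months | 12 mo | +3.4 to +6.5 | −2.4 to −1.6 | −0.7 to −0.4 |
| 6 months | 6 mo | +5.2 to +6.7 | +1.6 | −1.1 to −0.6 |
| 6 months | 12 mo | +4.2 to +7.5 | −0.9 to −0.2 | −0.7 to −0.3 |
| 36 months | 6 mo | +5.2 to +6.8 | +5.1 to +6.1 | −1.1 to −0.5 |
| 36 months | 12 mo | +5.3 to +8.6 | +5.1 to +7.4 | −0.6 to −0.4 |

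Moving the censoring date works at early cut-offs, with some over-correction at 12 months. With mature data it does almost nothing: most of these patients have died, and their deaths are events at the late death date. Only the last column brings 6-month PFS back to about 33–34%. Under other stopping patterns, censoring at the last assessment alone left 35–39% at earlier cut-offs and 41–42% at full follow-up, again at 30% stopping.

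**The case against.** The bias needs departures from the protocol. Scans are mandatory every 8 weeks until progression, on and off treatment, and with full compliance the two rules agree. Symptomatic deterioration and death from any cause are events, so many patients who stop scans because they are declining would be counted; the calculation leaves out symptomatic deterioration and so may overstate the size. The stopping rates are assumed. The bias is less than half the ±17-point half-width. All of this stands, and it limits the size, but it does not supply the missing rule.

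Three stronger readings are tempting and are not supported:

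- *That the idle contacts are survival contacts.* The Section 9.3 footnote schedules survival-status follow-up only after progression. Before progression the calendar asks for examination, disease assessment and imaging, and Section 14.4, item e, has the Follow-Up Form record how progression was determined. The gap comes only from Follow-Up Forms continuing on their own calendar when scans have lapsed.
- *That the plan judges PFS against a historical 3.6 months.* That figure is background. The historical-control hypotheses in Section 2.0 concern response rate, and Section 11.3 sets no PFS threshold.
- *That censoring at the last scan restores the true curve.* It does not in mature data, as the 36-month rows show.

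**Conclusion.** The point holds as a correctable weakness in a secondary endpoint. Section 10.5 uses a censoring date that carries no information about progression, and nothing else in the documents overrides it. If some patients stop scans while staying in contact, PFS is biased upward: about +1 to +8 points at 6 months for 5–30% stopping, and nil if nobody stops. The size rests on assumed stopping rates, exponential times and assumed survival after progression; the direction does not depend on those values. The primary response endpoint, the two-stage rule, its error rates and the sample size are unaffected.

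**What to change.** In Section 10.5:

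1. Censor living patients without documented progression or symptomatic deterioration at their last adequate disease assessment, or at registration if there is none.
2. Add a sensitivity analysis that also censors progression or death after two or more consecutive missed assessments at the last adequate assessment before the gap. Without this, most of the bias remains in mature data.
3. Report the last-contact version alongside, for comparison with any earlier trials of the group that used that rule, and state how many patients stopped scans before progression.

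The cost is a few sentences and some programming. Section 14.4, item d, already requires tumor assessments within 7 days, so no new data, visits or patients are needed. The downsides are slightly less follow-up, a departure from the present wording, and some risk of informative censoring if patients stop scans because they are worsening. That risk is why item 2 is a sensitivity analysis and not the main definition.

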10.6 Time to Death

From date of registration to date of death due to any cause. Patients last known to be alive are censored at date of last contact.

11.0 STATISTICAL CONSIDERATIONS

11.1 Accrual Goals

This study will initially be open to limited institutions, with an expected accrual of 3-12 patients in the D+G Phase I Portion and 6-18 patients in the D+T+G Phase I Portion. The Phase II Portion of the trial will be open Group-wide and will require 10-33 eligible patients. Assuming that 10% of patients enrolled will be ineligible or not evaluable,

approximately 70 patients will be required. Based on data from previous studies in similar patient populations the estimated accrual rate is 2-3 patients per month.

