- c. Patients should have a baseline fasting glucose level within the institutional upper limit of normal (IULN). This result should be obtained within 28 days prior to registration. Given the known metabolic toxicities of GSK2141795, patients with prior diabetes mellitus or problems in glucose control should have an HgA1c ≤ 7% within 28 days prior to registration. The same criterion will be used in patients with confirmed diagnosis of diabetes mellitus who have been on a stable dietary or therapeutic regimen for this condition in the last three months.
- d. Subjects should receive full supportive care during the study, including transfusions of blood and blood products, and treatment with antibiotics, antiemetics, anti-diarrheals, and analgesics, and other care as deemed appropriate, and in accordance with their institutional guidelines.
- e. Radiation skin injury has been reported with concurrent use of dabrafenib and radiation. Any radiation therapy should be completed at least two days prior to registration.
- 7.3 Treatment Phase I Dabrafenib + GSK2141795 (D+G)
 - a. Dose Escalation Scheme for D + G

Effective November 15, 2014, this trial will not proceed to the Phase II study of dabrafenib and GSK2141795, in favor of evaluation of triple therapy. (See Section 7.4).

This will be a dose-escalation clinical trial using a standard 3+3 design. There will be 2 dose levels. The starting dose level is 1. No patients will be enrolled in the next dose level until the toxicity is fully assessed after the completion of 2 cycles in at least 3 patients enrolled at the previous dose level. The maximum tolerated dose (MTD) is defined as the highest dose studied in which the incidence of dose-limiting toxicities (DLT) is < 33%. The cohort of the MTD (or proposed dose for Phase II Portion if MTD not reached) will be at least 6 patients.

Dose escalation scheme for D+G:

Dose Level	Dabrafenib (twice a day)	GSK2141795 (once a day)
1	150 mg	50 mg
2	150 mg	75 mg
2+	12/1/15	12/1/15

NOTE: The drug regimen will be given on an outpatient basis. A cycle equals 28 days.

In the case that the PK sampling suggests that there is a drug-drug interaction between dabrafenib and GSK2141795 resulting in decreased exposure of one or both of the study drugs, a cohort 2+ will be open with dosing increased over cohort 2 with goal of reaching the full dose plasma levels of both agents based on the prior single agent experience with each of them.

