 - 2. If 2 or more patients experience a DLT, lower dose levels may be investigated to find the recommended dose for the Phase II Portion or the study may be permanently closed.

c. Definition of Dose-Limiting Toxicity

Toxicities will be graded according to the NCI Common Terminology Criteria for Adverse Events Version 4.0.

Dose-limiting toxicities (DLT) apply only during Cycles 1 and 2 and should be drug-related (possible, probable or definite). The following events are considered dose limiting:

- 1. Febrile neutropenia,
- 2. Grade 4 neutrophil count decrease for more than 7 days duration,
- 3. Grade 4 platelet count decrease,
- 4. Grade 3 or 4 skin rash, fevers and hyperglycemia that do not recover within 14 days with adequate medical management as described in Section 8.0,
- 5. Grade 3 or 4 non-hematologic toxicity that does not recover within 7 days with adequate medical management.

7.4 Treatment - Phase I Dabrafenib + Trametinib + GSK2141795 (D + T + G)

a. Dose Escalation Scheme of D + T + G:

Phase I portion: The primary objective is to assess the safety of dabrafenib, trametinib, and GSK2141795 in combination and to determine the dosing of the 3 drug combination for the Phase II portion. Dose escalation of dabrafenib, trametinib, and GSK2141795 will be initiated after completion of the dabrafenib + GSK2141795 phase I dose escalation. This three drug dose escalation will follow a standard 3+3 design. There will be 4 dose levels. No patients will be enrolled in the next dose level until the toxicity is fully assessed after the completion of 2 cycles in at least 3 patients enrolled at the previous dose level. The maximum tolerated dose (MTD) is defined as the highest dose studied in which the incidence of dose-limiting toxicities (DLT) is < 33%. The MTD cohort (or proposed dose for Phase II portion if MTD not reached) will include at least 6 patients.

Dose escalation scheme for D+T+G

	Dabrafenib	Trametinib	GSK2141795
Dose Level	(mg PO BID)	(mg PO daily)	(mg PO daily)
1	150	1.5	25
2	150	1.5	50
3	150	1.5	75
4	150	2	75

b. Dose Determination Rules

- 1. Dose Limiting Toxicity (DLT) is defined in Section 7.4c.
- Only DLTs occurring during Cycles 1 and 2 will be used to guide dosing determination of the study combinations.
- 3. Patients will be considered evaluable for DLT if they fulfill one of the following criteria:
 - They experience a DLT or

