 - They received GSK2141795 at the assigned dose for at least 11 days during Cycle 1, at least 28 days combined of trametinib over Cycles 1 and 2, and at least 28 days of dabrafenib over Cycles 1 and 2 or
 - They received GSK2141795 at the assigned dose for at least 11 days during Cycle 1, at least 50% of trametinib during Cycle 1 and at least 50% of dabrafenib during Cycle 1.

Patients who do not meet at least one of these criteria will be considered not evaluable for DLT and will be replaced.

- 4. The following dosing scheme will be used for dose determination:
 - a. Begin at Dose Level 1 (see Dose Escalation Scheme above):
 - 1) Enroll 3 patients and evaluate for toxicity. Enroll additional patients as required until 3 evaluable patients have been enrolled.
 - 2) If 0 of the initial 3 patients experience a DLT stop enrollment at this dose and continue to the next higher dose level. If the current dose level is Dose Level 4, then expand enrollment until 6 evaluable patients have been enrolled or two patients experience a DLT.
 - 3) If 0-1 out of 6 patients experience a DLT on Dose Level 4, then Dose Level 4 is the MTD.
 - 4) If only 1 of the initial 3 evaluable patients at the current dose level experience a DLT, expand enrollment until 6 evaluable patients have been enrolled or a second patient experiences a DLT.
 - 5) If 1 of 6 patients experiences a DLT, continue to the next highest dose level. If 2 or more patients have already experienced a DLT at the next highest level or if the current dose level is Dose Level 4 then the current dose level is the MTD.
 - 6) If 2 or more patients experience a DLT, stop enrollment at the current dose level and continue to the next lowest dose level. If 6 patients have already been enrolled at the next lowest dose level then that dose level is the MTD. If the current dose level is Dose Level 1 lower dose levels may

be investigated to find the recommended dose for the Phase II Portion or the study may be permanently closed.

c. Definition of Dose-Limiting Toxicity

Toxicities will be graded according to the NCI Common Terminology Criteria for Adverse Events Version 4.0.

Dose-limiting toxicities (DLT) apply only during Cycles 1 and 2 and should be drug-related (possible, probable or definite). The following events are considered dose limiting:

- 1. Febrile neutropenia,
- 2. Grade 4 neutrophil count decrease for more than 7 days duration,
- 3. Grade 4 platelet count decrease,

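### The upper accrual figure of 18 for D+T+G Phase I in Section 11.1 is below the 24 evaluable patients that the four-level 3+3 design can need, and the total of about 70 inherits the shortfall

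*Combined protocol and SAP*

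**What the plan says.** Section 11.1 gives expected accrual of "3-12 patients in the D+G Phase I Portion and 6-18 patients in the D+T+G Phase I Portion", and states that Phase II "will require 10-33 eligible patients". It then makes an allowance, "Assuming that 10% of patients enrolled will be ineligible or not evaluable", and on that footing concludes that "approximately 70 patients will be required".

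Sections 7.3 and 7.4 describe the two dose escalations:

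- For D+G, Section 7.3a says "There will be 2 dose levels".
- For D+T+G, Section 7.4a says "There will be 4 dose levels", and its table lists all four.
- Section 7.4b expands any D+T+G level with one DLT in three patients to a cohort of six, stopping early at a second DLT. The rule begins: "If only 1 of the initial 3 evaluable patients at the current dose level experience a DLT, expand enrollment until 6 evaluable patients have been". One DLT in six then leads to the next level.
- The top level is expanded even after a clean first cohort: "If the current dose level is Dose Level 4, then expand enrollment until 6 evaluable patients have been enrolled or two patients experience a DLT".
- Patients who are not evaluable for DLT are replaced, so these counts are of evaluable patients.

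Section 11.3b sizes Phase II as 10 eligible patients, then 23 more.

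**The concern.** An accrual section should cover the design that it describes. Two of the three upper figures in Section 11.1 are the most patients that their part of the trial can use. The third, for D+T+G, is the figure for a scheme with one level fewer than Section 7.4 contains. Because the total is the sum of the upper figures divided by 0.9, the shortfall passes into it. At stake is whether the stated sample size agrees with the escalation rules. The validity of the escalation and of the Phase II test is not in question.

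**Working it through.** **1. Reproduce the stated total.** Inputs from Section 11.1: upper figures 12, 18 and 33; allowance 10%.

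- 12 + 18 + 33 = 63
- 63 / 0.9 = 70.0 (63 x 1.1 = 69.3 also rounds to 70)

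So the 70 is the sum of the three upper figures, inflated for the 10%.

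**2. See where each upper figure comes from.**

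| Part | Rule | Most patients under the rule | Section 11.1 |
|---|---|---|---|
| D+G Phase I | 2 levels x 6 (7.3) | 12 | 12 |
| D+T+G Phase I | 4 levels x 6 (7.4) | 24 | 18 |
| Phase II | 10 + 23 (11.3b) | 33 | 33 |

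A path to 24 is one DLT among the first three patients and none among the next three at each of Levels 1, 2 and 3, followed by completion of Level 4: 6 + 6 + 6 + 6 = 24. Nothing in Section 7.4b stops enrolment at 18. The stated 18 equals 3 x 6.

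**3. Recompute the total on the same basis.**

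- 12 + 24 + 33 = 69
- 69 / 0.9 = 76.7, about 77 (69 x 1.1 = 75.9)
- Difference from 70: 7 patients, or 10%

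**4. How often it would matter.** The documents give no DLT rates, so those below are assumptions. All paths of the Section 7.4b rules were enumerated exactly in cohorts of three, including expansion of a lower level after a failed one. For the combined Phase I column, the first two rates in each row were also applied to D+G, and the two escalations were treated as independent. The combined budget is 12 + 18 = 30.

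| Assumed DLT rates, Levels 1-4 | Mean D+T+G size | P(D+T+G > 18) | P(D+T+G = 24) | P(both Phase I parts > 30) |
|---|---|---|---|---|
| 5% at all levels | 15.7 | 4.1% | 0.2% | 0.7% |
| 10% at all levels | 15.2 | 9.0% | 0.8% | 2.6% |
| 5/10/15/20% | 15.9 | 10.0% | 0.8% | 2.5% |
| 10/15/20/30% | 14.8 | 12.2% | 1.5% | 4.4% |

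Whole cohorts of three slightly overstate the count on paths where a second DLT stops a cohort early. The maximum of 24 is not affected.

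**5. The overall budget of 63.** To pass 63, Phase II must also reach its second stage, because 12 + 24 + 10 = 46 is below 63. The chance of at least 2 responses in 10 is 1 - 0.85^10 - 10 x 0.15 x 0.85^9 = 46% at a true response rate of 15%, and 91% at 35% by the same formula. Multiplying, and assuming independence, the chance of passing 63 runs from 0.7% x 46% = 0.3% to 4.4% x 91% = 4.0%.

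**The case against.** The best defence is the wording. Section 11.1 calls the Phase I ranges expected accrual and the total approximate, and an expected range need not reach the longest path. Under the assumed rates, 18 covers about 88-96% of D+T+G paths. The total is safer still, because it also budgets D+G at its maximum.

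This limits the weight of the point but does not remove it. With a mean of about 15-16 patients in the four scenarios, 18 is not an expected value, and it is not the maximum either. The figures it is added to are maxima. The 10% allowance does not fill the gap, since it is already used in reaching 70 and is meant for ineligible or non-evaluable patients.

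Three stronger readings are tempting, and the documents do not support them:

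- **Extra Phase I patients would take Phase II places or force an amendment.** Nothing makes 70 a cap shared between the phases. Phase II has its own size, Phase I patients are excluded from its analysis (Section 11.3b), and Section 7.4b directs expansion and replacement without reference to 70.
- **The lower figure of 6 is also wrong.** It can be read as the minimum MTD cohort, which Section 7.4a sets at six. It does not enter the 70.
- **77 should replace the 97 in the Section 2.0 table of anticipated accrual by ethnicity, race and sex.** The source of the 97 is not stated, and it matches neither 70 nor 77. It is a separate discrepancy.

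**Conclusion.** The inconsistency is real and small. As written, Section 7.4 can need 24 evaluable D+T+G patients where Section 11.1 allows 18. On Section 11.1's own method, the total is about 77 instead of about 70. These two results rest only on the documents' rules and arithmetic.

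The likelihoods rest on assumed DLT rates: about 4-12% for needing more than 18 D+T+G patients, and about 1-4% for exceeding the pooled Phase I budget of 30. Phase II size, alpha, power and decision rule do not change, nor do the escalation rules.

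The documents do not say how 18 arose. A reader might infer that it was carried over from a three-level scheme. The number fits that, but nothing confirms it.

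Nor is 77 an absolute ceiling. It leaves out the optional D+G cohort 2+ (Section 7.3a), any lower dose levels investigated after DLTs at Level 1 (Sections 7.3b and 7.4b), and any additional intensive-PK patients (Section 15.3c).

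**What to change.** In Section 11.1, restate the upper figure for D+T+G Phase I as 24 evaluable patients and the total as about 77, showing (12 + 24 + 33)/0.9. Add one sentence saying that these figures exclude the optional D+G cohort 2+, any lower dose levels and any additional intensive-PK patients.

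Separately, establish where the total of 97 in the Section 2.0 table comes from and reconcile it with Section 11.1. Do not simply overwrite it with 77.

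The cost is two numbers and a sentence. The stated total rises by 7 patients, and the design, the expected enrolment and the Phase II operating characteristics stay as they are.
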